NCT05166356

IRB# 21-007898

Describing the Determinants and Effects of Variation in the Adoption a Use of the NOHARM Pain Management Intervention Among Diverse Surgical Practices

September 11, 2023 V8

IRB Minimal Risk Protocol Template

General Study Information

Principal Investigator: [name], MSCE

Study Title: Describing the Determinants and Effects of Variation in the Adoption a Use of the NOHARM Pain Management Intervention Among Diverse Surgical Practices

Protocol version number: September 11, 2023 Version 8

Research Question and Aims

Background and Introduction

NOHARM (Non-pharmacologic options in post-operative and hospital-based rehabilitation and pain management pragmatic trial) is a National Institutes of Health (NIH)-funded pragmatic trial testing whether patient education about non-pharmacologic pain management options, coupled with support from ambulatory and inpatient surgical care teams, improves pain and function while avoiding opioid overuse in the post-operative setting. This trial is currently being conducted among diverse surgical practices across the Mayo Clinic Enterprise as part of a stepped wedge, clusterrandomized pragmatic trial (IRB# 20-004839) with the implementation scheme depicted below (see Figure 1).

Figure 1: Surgical	practices in the NOHARM Trial
--------------------	-------------------------------

	Tranche 1 Rochester Cardiac, C-Section Florida Ortho Eau Claire Ortho, Colorectal, Gyn, C-section LaCrosse Gyn, C-Section	Tranche 2 Rochester Ortho, Gyn, Lung Arizona Lung, Cardiac Mankato Colorectal	Tranche 3 Rochester Colorectal Florida Transplant Arizona Colorectal, Gyn, Transplant	Tranche 4 Florida Colorectal, Gyn, Lung, Cardiac Eau Claire Lung, Cardiac Mankato C-Section	Tranche 5 Rochester Transplant Arizona Ortho Mankato Ortho LaCrosse Ortho, Colorectal
condition	Data Collection 10/16/2020				
Step 1	Go live 3/1/2021				
Step 2		Go live 10/1/2021			
Step 3			Go live 5/1/2022		
Step 4				Go live 12/1/2022	
Step 5					Go live 7/1/2023

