Once data has been rapidly analyzed, we may return to the transcripts for more in depth analysis consisting of regular meetings, code book drafting and revision, coding of transcripts, resolving differing interpretations by consensus, running coding queries in Nvivo, memo summarization, and subsequent synthesizing into themes. This will enable a more in-depth assessment of the barriers and facilitators to implementation practices experienced.

Inpatient Stakeholder Surveys

We will also give inpatient stakeholders the opportunity to share feedback on their thoughts about the intervention via a short survey consisting of mostly multiple choice questions, which should take approximately 5 minutes to complete. The survey will ask about stakeholders' role and Mayo Clinic site they work at, which will allow us to agreggrate data at the site level, but will maintain the anonymity of individual's responses. We will ask stakeholders' about their impressions about the added value and burden of the intervention, to what extent they have encouraged their staff to support the intervention, and to what extent they would like to see the intervention become part of practice. These survey responses will help us understand to what extent inpatient allied health nursing leaders (e.g., nurse managers, interim nurse managers, clinical nurse specialists, nursing education specialists) at different sites support the intervention, which is likely to impact staff's uptake of the intervention and impact staff intervention fidelity.

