Using procedures like those of Aim 1, we will create automated Epic reports that summarize care team fidelity to the NOHARM intervention. Specifically, we will use these reports to identify the proportion of NOHARM patients who are discharged from a practice with NPPC selections documented in flowsheet rows and the proportion of patients for which at least some of the Healing After Surgery education listed in the Education Tab has been delivered. We will then rank order practices based on the proportion of patients who did not have NPPC selections in their chart at the time of surgery, but were discharged with NPPC selections, and the proportion of patients who had at least some Healing After Surgery education delivered by the time of discharge to identify the top 10 and bottom 10 performing practices interviewed. The proportion of patients discharged with NPPC selections is a good proxy for inpatient care team fidelity because this data point can be reliably captured and Healing After Surgery education points auto-populate for all patients, so we can evaluate whether they have been completed or not.

Analysis: After, we have identified the practices with the highest and lowest fidelity, we will create a new data matrix with the qualitative interview data from the 10 highest and lowest fidelity practices and identify differences in themes between the highest and lowest performing practices organized according to CFIR constructs. We will also compare the CFIR construct ratings between high and low fidelity sites to determine whether ratings (perceived barriers and facilitators pertaining to the different constructs) differentiate inpatient practices with high verus low fidelity.

Physical and Occupational Therapy

To understand barriers and facilitators to implementation and adoption of the NOHARM intervention by physical and occupational therapy teams, we will administer an anonymous web-based survey (RedCAP). The survey will take approximately 10 minutes to complete and consist of multiple-choice questions along with a few open-ended questions for therapists to provide additional feedback if they wish. We will ask staff which Mayo Clinic location they work at, but no other identifying information will be collected.

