We will recruit physical and occupational therapists, by working with therapy leaders and requesting ~15 minutes on standing therapy meetings (~2 minutes to introduce the survey and ~10-13 minutes to allow time for survey completion). After introducing the survey, we will share the link to the survey in the chat so that staff who are interested in completing the survey can do so. Paper copies may also be supplied for in person meetings. For therapy leaders who prefer not to offer the opportunity to participate during a staff meeting, we will ask them to distribute an email invitation inviting staff to participate in the survey, which will contain the survey URL. We will ask that leaders share meeting attendance or staff distribution lists with our team so we can calculate a response rate, but due to the anonymous nature of the survey, we will not be able to identify which staff member chose to participate and who did not. We seek to recruit a total of n = 280 therapists.

Epic Reports: To distinguish between high and low fidelity therapy practices, we will pull Epic report data on therapists' interaction with the NOHARM therapy identifier (BPA=Best Practice Advisory) and use of the NOHARM therapy smartphrase within their documentation. We will then rank order therapy practices from highest to lowest fidelity according to the frequency by which therapists acknowledge the NOHARM BPA and the frequency with which therapists documented supporting the patient's NOHARM non-pharmacologic pain care preferences during their therapy sessions, using the NOHARM therapy smart phrase.

Analysis: We will explore differences in survey responses between high and low fidelity therapy practices identified by the Epic reports to determine whether certain barriers or facilitators were more common amongst high or low fidelity practices.

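### Can anonymous therapist survey answers be compared by therapy practice when location is the only linking field stated?

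*Protocol*

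**What the plan says.** The point concerns the Physical and Occupational Therapy part of Aim 3, the only part of the protocol that surveys therapists. The survey is anonymous and web-based, with paper copies possible at in-person meetings. On identifying fields the protocol says: "We will ask staff which Mayo Clinic location they work at, but no other identifying information will be collected". Therapists are reached through therapy leaders, at standing meetings or by forwarded email. Leaders are also asked for lists, but for a different purpose: "We will ask that leaders share meeting attendance or staff distribution lists with our team so we can calculate a response rate". The recruitment target is 280.

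Separately, Epic data on therapists' responses to the NOHARM advisory and their use of the NOHARM smartphrase are used to "rank order therapy practices from highest to lowest fidelity". The analysis joins the two sources: "We will explore differences in survey responses between high and low fidelity therapy practices identified by the Epic reports". The protocol does not say what a therapy practice is or how many there are.

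**The concern.** To compare survey answers by fidelity group, each anonymous answer must be assigned to a unit that the Epic reports have ranked. Location is the only stated field that could do this, and the word practice usually means something narrower in this protocol. Figure 1 lists surgical practices by discipline within site. The Inpatient Epic Reports section ranks those practices to "identify the top 10 and bottom 10 performing practices interviewed", which six sites could not supply. A reader who carries that meaning over to therapists would conclude that the planned comparison cannot be made from the data described.

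The worry is about data collection, which is why leaving the detail to an analysis plan does not dispose of it at once. The protocol accepts that individual responders cannot be identified, so a team field missing from the survey could not be reconstructed from attendance or distribution lists. The time of up to 280 therapists could then yield answers that do not serve the one comparison planned for them.

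**Working it through.** The protocol gives no figure for this comparison that could be reproduced. The target of 280 comes with no number of units, effect size, error rate or power. The check is therefore mainly one of reading the sections side by side, with a short count.

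**Number of sites.** Counting discipline-by-site entries in Figure 1 across the five tranches:

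- Rochester: 2 + 3 + 1 + 1 = 7
- Florida: 1 + 1 + 4 = 6
- Eau Claire: 4 + 2 = 6
- Arizona: 2 + 3 + 1 = 6
- La Crosse: 2 + 2 = 4
- Mankato: 1 + 1 + 1 = 3

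The total is 7 + 6 + 6 + 6 + 4 + 3 = 32. This agrees with the 32 practices stated elsewhere in the protocol and places them in six sites. The count describes surgical practices. It says nothing direct about how therapists are organised.

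**If a therapy practice is finer than location.** Answers cannot be assigned from the stated field. For this to be a defect, two things must hold: therapy units are narrower than location, and the survey carries no non-identifying team item. No section says that therapists are divided by surgical discipline. The sentence on fields rules out only other identifying information, and the multiple-choice items are not shown. Neither condition is established.

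**If a therapy practice is a location.** Each answer links directly to a ranked unit. With about six sites, an even spread would give 280 / 6 = 46.7 therapists per site. Both the six sites and the even spread are assumptions: the therapist section gives no number of locations.

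**Which reading the text favours.** Four features bear on this.

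- Location is the field the designers chose to collect, which makes most sense if answers are to be grouped by it.
- Recruitment runs through therapy leaders and therapy meetings. The nursing leader survey, by contrast, recruits from all 32 clinical practices.
- Even so, that nursing survey is summarised by site. It collects "role and Mayo Clinic site they work at, which will allow us to agreggrate data at the site level". The protocol's other staff survey in Aim 3 is therefore handled at the level of site.
- The word practice is not used strictly. After ranking surgical practices, the Inpatient Epic Reports analysis proposes to "compare the CFIR construct ratings between high and low fidelity sites", meaning the same groups.

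Together these favour location. They do not prove it.

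**The case for a change.** The strongest argument for a change is that neither reading is entirely comfortable. A finer unit breaks the linkage beyond later repair. A location-level unit leaves about six units, so any difference in reported barriers between high and low fidelity groups is mixed with everything else that differs between sites. One defining sentence would cost almost nothing, and a team item or a survey code per team would protect the finer comparison if that is what is wanted.

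Much of this is correct. The term is undefined, a field not collected in an anonymous survey is lost, and six sites cannot separate fidelity from site. It still falls short of requiring a change. The irrecoverable loss depends on two facts that the protocol does not state. The site confounding would count against a claim to have identified causes, but the protocol says only that differences will be explored, to see whether some barriers or facilitators were more common in one group. That is a descriptive aim, and advice to report descriptively largely repeats it. A team item would reduce anonymity, most of all in small teams, in a survey of staff about their own practice. Collecting location alone is a reasonable choice when candour matters. How units are grouped and summarised is also ordinary material for an analysis plan, which is not at hand.

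**Conclusion.** The observation is accurate: the protocol leaves therapy practice undefined, and location is the only linking field it states. It is not a contradiction. On the better-supported reading, in which the unit is location, the comparison can be made as described. It rests on about six sites, with about 47 therapists each under an even spread, and is descriptive, as the protocol's own wording implies. An analyst holding a location field and a ranking from Epic would rank and summarise by location without further instruction.

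No change to the plan follows. The conclusion rests on two assumptions: that the therapy unit is location, and that the therapist locations are the six sites in Figure 1. If the investigators meant a finer unit and the survey has no team item, the comparison at that level could not be made. Nothing in the protocol shows that they did. The matter is one of missing detail in an exploratory component, and small.
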